**BOTE Inflammation Score**

Score	Global Assessment	Description
0	No inflammation	No evidence of local inflammation
1	Mild	Minimal erythema and/or edema
2	Moderate	Definite erythema and/or edema with or without hemorrhagic crusting
3	Severe	Erythema and edema with definite hemorrhagic crusting
4	Very severe	Strong reaction spreading beyond the treated area, bullous reaction, erosions

**LSR Score**

Score	Erythema	Flaking/Scaling	Crusting	Swelling	Vesiculation/Pustulation	Erosion/Ulceration
0	Not present	Not present	Not present	Not present	Not present	Not present
1	Slightly pink	Mild, limited	Isolated crusting	Minimal, limited	Fine vesicles	Superficial erosion
2	Pink or light red	Moderate	Crusting < 50%	Mild, palpable	Scant transudate or exudate	Moderate erosion
3	Red, restricted to treatment area	Coarse	Crusting > 50%	Moderate	Moderate transudate or exudate	Marked, extensive
4	Red extending outside treatment area	Scaling extending outside treatment area	Crusting extending outside treatment area	Marked swelling extending outside treatment area	Marked transudate or exudate	Black eschar or ulceration

Adverse events will be assessed and collected after the initiation of study drug treatment through the end of the subject’s last visit. Treatment-related AEs and all serious adverse events will be followed up until resolution or up to one year after last treatment, whichever is sooner.

Scar formation (scars/keloids/hypertrophic scars) will be assessed starting at the Week 4 visit through Week 24. The investigator will map locations of the molluscum lesions at Baseline. Additional lesions identified through Week 12 will be added to the map. Using the map as a guidance, the investigator will assess the treated areas for scar/keloid formation. All scars, including keloid/hypertrophic scars, that develop after the Baseline assessment should be captured as AEs and assessed for relatedness to study treatment.

If a subject's treatment is discontinued by the investigator or the subject because of an AE, that AE should be indicated as the reason for treatment discontinuation. All subjects will be encouraged to remain in the study and to complete all required study visits throughout the 24-week study duration.

When approximately 200 subjects are randomized, a data safety monitoring board (DSMB) will review all available unblinded safety data (including completed patch testing results). The DSMB will provide their recommendation for the study to proceed or not proceed.

## 5. DETERMINATION OF SAMPLE SIZE

Approximately 850 subjects, 6 months of age and older, with a minimum of 3 and a maximum of 70 MC lesions at Baseline will be randomized in a 1:1 (active:vehicle) scheme. The sample size assumptions for this study were informed by the integration of the completed phase 3 studies [NI-MC301](#) and [NI-MC302](#). Multiple replications of simulated random sampling of the integrated NI-MC301 and NI-MC302 data was performed to ensure the sample size assumptions align with the proposed design of NI-MC304. This includes the 1:1 ratio (active:vehicle) and the percentages observed in NI-MC301 and NI-MC302 for each stratum of each of the stratification factors: investigator type, number of randomized subjects per household, and baseline BOTE score that are planned for NI-MC304.

The analysis of the proportion of subjects with complete response of all treatable MC at Week 12 within the Intent-to-Treat (ITT) Population of the multiple replications of simulated random sampled integrated data yields rates of 20% for vehicle and 29.5% for SB206 10.3% QD with the covariate-adjusted treatment difference was 9.5%. A sample size of 850 subjects (425 subjects in the SB206 10.3% QD group and 425 subjects in the vehicle group) will provide 90% power for a 2-sided alpha test of size 0.05 to detect an absolute difference of 9.5% when the vehicle response rate is 20%.

Simulations were performed with 10,000 replications to confirm the accuracy of these power estimates (i.e., true power and simulation based estimate of power) and to provide simulated median, 10% percentile and lowest detectable treatment difference estimates for a sample size of 850 subjects.

At the two-sided  $\alpha=0.05$  level, the median detectable treatment difference is approximately 9.9% with a simulation based estimated power of 88%. The tenth percentile for detectable treatment difference is 7.1%, thus approximately 90% of the simulations with two-sided  $p < 0.05$

produced an estimated treatment difference exceeding 7.1%. The lowest detectable treatment difference is 5.7%.

At two-sided alpha levels  $<0.05$ , for example,  $p=0.025$  level, the median detectable treatment difference is approximately 10.2% with a simulation based estimated power of 82%. The tenth percentile for detectable treatment difference is 7.7% and a lowest detectable difference of 6.5%.

## 6. GENERAL ANALYSIS CONSIDERATIONS

The statistical analyses will be reported using summary tables, listings, and figures (TLFs). The International Council for Harmonisation (ICH) numbering convention will be used for all TLFs. Unless otherwise noted, all statistical testing will be two-sided and will be performed at the 0.05 significance level. Tests will be declared statistically significant if the calculated  $P$ -value is  $\leq 0.05$ .

Continuous variable summaries will include the number of subjects ( $n$ ) with non-missing values, mean, standard deviation (SD), median, minimum, and maximum. Other statistics such as quartiles, confidence intervals (CIs), and number of missing values may be added as appropriate.

Categorical variable summaries will include the frequency and percentage of subjects who are in the category or each possible value. In general, the denominator for the percentage calculation will be based upon the total number of subjects in the study population within each treatment group, unless otherwise specified. The denominator for by-visit displays will be the number of subjects in the relevant study population with non-missing data at each visit.

All summary tables will be presented by treatment group. Baseline summaries will also include an overall summary column.

Individual subject data obtained from the eCRFs and any derived data will generally be presented by subject in data listings. Additionally, a listing of the subjects requiring a narrative because they experience one of the following events: serious adverse event, death, discontinued the study due to an AE, hypertrophic or keloid scarring, unresolved scars, or LSR suggestive of allergic contact dermatitis will be presented.

A separate report for the results from the study exit interview will be created.

The analyses described in this plan are considered a priori, in that they have been defined prior to breaking the blind.

Any analyses performed subsequent to breaking the blind will be considered post hoc and exploratory. Post hoc analyses will be labeled as such on the output and identified in the clinical study report.

All analyses and tabulations will be performed using SAS® software Version 9.4 or higher. Tables, listings, and figures will be presented in RTF format.

The process for SAS program validation and quality control (QC) for programs and outputs is documented in the Synteract working instruction “SAS programming quality control.” Study-specific QC requirements can be found in Appendix B: SAS Programming QC Requirements.

The study treatment period is defined from randomization through completion of Week 12/ET1 visit and the safety follow-up period is from the completion of Week 12 through the completion of Week 24/ET2 visit.

After all subjects have completed their Week 12/ET1 visit, thus completing the Treatment Period of the study, the database through Week 12/ET1 will be frozen and unblinded for purposes of the primary analysis of efficacy and safety. While this analysis is being prepared, the subjects will continue through Week 24/ET2. After all subjects have completed their Week 24/ET2 visit, the database will be locked and the follow-up data will be analyzed.

## 7. NOTATION OF TREATMENT GROUPS AND VISITS

### Analysis visits

Baseline is defined as the last non-missing value recorded prior to the first application of study drug. If time is not recorded and the assessment was on the same day as the first application of study drug, then it will be assumed the assessment occurred prior to the application of study drug. The baseline record will have an analysis visit of “Baseline”. If a subject was randomized but not treated, then baseline is defined as the last non-missing value on or before the date of randomization.

For analysis of lesion counts, if there are multiple assessments of differing assessment types (remote vs in-clinic) within a given window, then the in-clinic lesion count will be used for analysis. For all evaluations of all parameters, assessments will be analyzed according to the visit at which they occurred (i.e., per the eCRF visit label). In order to account for the fact that the Week 12 and Early Termination visits are collected on the same eCRF in the database, a check against the Study Exit form will be made to determine if the visit is a Week 12 or an Early Termination Visit. If the visit is an Early Termination visit, then the visit will be mapped according to the table below. If there is no corresponding Study Exit form on the same date, then it will be considered a Week 12 visit. If there is no assessment in a given visit, then the following visit windows will be applied to determine if an unscheduled visit may be used:

Visit	Analysis Visit	Target Study Day	Study Day Analysis Window
Week 2 (±3 days)	Week 2	15	Day 12 to 22
Week 4 (±5 days)	Week 4	29	Day 23 to 43
Week 8 (±5 days)	Week 8	57	Day 44 to 71
Week 12 (±5 days)	Week 12	85	Day 72 to 98
Week 16 (±7 days)	Week 16	113	Day 99 to 126

Visit	Analysis Visit	Target Study Day	Study Day Analysis Window
Week 20 ( $\pm 7$ days)	Week 20	141	Day 127 to 154
Week 24 ( $\pm 7$ days)	Week 24	169	Day 155 to 182

Days are measured from the date of randomization. Study days corresponding to measurements are calculated as:

- Assessment date – date of randomization + 1, if assessment date is on or after the date of randomization.
- Assessment date – date of randomization, if measurement date is before the date of randomization.

In the event of multiple unscheduled records falling in the same analysis window, the assessment which is closest to the target study day will be chosen for analysis.

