6.7.7 Visit 6/Week 12/ET (Day 85 ±5 days) (In-clinic Visit)

The following procedures must be performed and recorded at the Week 12/ET visit.

1. Obtain pregnancy test and evaluate results, as applicable.
2. Perform BOTE Inflammation Score.
3. Perform Local Skin Reaction Assessment.
4. Perform lesion counts and update lesion map with location for any new lesions.
5. If previously cleared, assess for subject recurrence of MC.
6. Perform scarring/keloid assessment; if present, document location on lesion map and record as an AE.

7. Perform a brief physical examination.
8. Complete Investigator Global Severity Assessment and Investigator Global Impression of Change Assessment.
9. Complete Subject Global Severity Assessment and Subject Global Impression of Change Assessment.
10. Subject/caregiver administer final dose of study drug from previously dispensed kit only if lesions are present.
11. Weigh returned study drug and review study compliance.
12. Collect and record AE information for AEs reported.
13. Update concomitant medication information and confirm if any new occurrences of MC were reported in the subject's household.
14. Review interview procedures with the subject/caregiver and obtain documented ICF/assent.

Note: Follow up interviews will be performed with a subset of subjects that complete Week 12. Consent will be obtained during the Week 12 visit, and the follow up interview will be performed with the subject/caregiver at a later date.

**6.7.8 Visit 7/Week 16 and Visit 8/Week 20 (Day 113 ±7 days; Day 141 ±7 days)
(Telephone Contact)**

The following procedures must be performed and recorded at the Week 16 and Week 20 visits. It is expected that these visits should be done by telephone.

1. Collect and record information for new and ongoing AEs, including recurrence of MC.
2. Confirm household MC status (any new cases in household members since last visit).
3. Update concomitant medication information.

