## 10.1 Efficacy Endpoints

The primary efficacy endpoint is the proportion of subjects with complete clearance of all treatable MC at Week 12.

The secondary efficacy endpoints are the following:

- 1) Proportion of subjects achieving a lesion count of 0 or 1 of all treatable MC at Week 12.
- 2) Proportion of subjects achieving at least a 90% reduction from Baseline in the number of all treatable MC at Week 12.
- 3) Proportion of subjects with complete clearance of all treatable MC at Week 8.
- 4) Percent change from Baseline in the number of all treatable MC at Week 4.

Complete clearance is defined as having a total number of lesions count of 0.

The exploratory endpoints are the following:

- Percent change from Baseline in number of treatable MC at each visit (Weeks 2, 8, 12)
- Proportion of subjects achieving a lesion count of 0 or 1 of all treatable MC at Weeks 2, 4, and 8
- Proportion of subjects achieving at least a 90% reduction from Baseline in the number of all treatable MC at Weeks 2, 4, and 8
- Proportion of subjects achieving at least a 75% reduction from Baseline in the number of all treatable MC at Weeks 2, 4, 8, and 12
- Absolute change from Baseline in number of treatable MC at Weeks 2, 4, 8, 12
- Proportion of subjects with complete clearance of all treatable MC at Week 2 and Week 4 visits
- Time to complete clearance of all treatable MC, defined as the days between the date of first dose and the first date of clearance. Subjects who do not achieve complete clearance will be censored at the date of the last lesion count assessment.
- Proportion of subjects who have a recurrence of MC after the first visit at which complete clearance was observed, defined as the total lesion count being greater than 0 at any point after achieving a count of 0
- Subject-reported spread to household members as measured by any new occurrence of MC in household members of subjects at each visit (Weeks 2, 4, 8, 12)
- Investigator Global Severity Assessment at Baseline, Week 12, and Week 24
- Subject Global Severity Assessment at Baseline, Week 12, and Week 24
- Investigator Global Impression of Change at Week 12 and Week 24

- Subject Global Impression of Change at Week 12 and Week 24

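### Global severity and change ratings collected at an early termination visit before Day 72 drop out of the Week 12 summaries, and the SAP does not say how ET2 ratings are assigned

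*SAP*

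**What the plan says.** **Collection.** Protocol 6.7.7 (Week 12/ET) includes "Complete Subject Global Severity Assessment and Subject Global Impression of Change Assessment", and the same list has the two investigator ratings. The schedule in Protocol 1.2 marks all four under Week 12/ET1 and again under Week 24/ET2.

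**Endpoints.** SAP 10.1 lists "Subject Global Severity Assessment at Baseline, Week 12, and Week 24" and "Subject Global Impression of Change at Week 12 and Week 24", with matching investigator versions. No other time points are defined.

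**Visit assignment.** The default in SAP 7 is: "For all evaluations of all parameters, assessments will be analyzed according to the visit at which they occurred (i.e., per the eCRF visit label)". An exception follows, introduced by "In order to account for the fact that the Week 12 and Early Termination visits are collected on the same eCRF in the database". The form is checked against the Study Exit form. When it proves to be a termination visit, "If the visit is an Early Termination visit, then the visit will be mapped according to the table below". Otherwise, "If there is no corresponding Study Exit form on the same date, then it will be considered a Week 12 visit".

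**Denominators and missing data.** SAP 6 states: "The denominator for by-visit displays will be the number of subjects in the relevant study population with non-missing data at each visit". SAP 10.4 counts missing as non-response only in analyses based on response. SAP 11.3 gives no last-rating rule and no missing category for the global ratings.

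**The concern.** The day-based mapping suits lesion counts, which are scheduled at Weeks 2, 4 and 8. It does not suit ratings that have no such visits. A leaver's rating is collected, moved to a visit where nothing is summarized, and then removed from the Week 12 denominator.

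These ratings show whether the lesion result corresponds to something that subjects and investigators perceive. The Week 12 outputs affected are the severity shift tables, the Impression of Change summaries, the cumulative distribution plots, the Improved versus Not Improved displays and the correlations with baseline lesion count. On the response endpoints the same leavers stay in the ITT denominator as non-responders, so the two sets of results describe different groups of subjects.

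**Working it through.** The plan gives no figure for the global ratings, so there is none to reproduce. The check traces the rule and then sizes it under stated assumptions.

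**1. Where an ET1 rating goes.** The windows come from the SAP 7 table. Day 1 is randomization and Week 12 is Day 85, so pre-Week-12 exits are taken as Days 2 to 84, which is 83 possible days. A same-day Study Exit form is assumed.

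| ET1 study day | Days | Analysis visit | Rating endpoint defined there? |
|---|---|---|---|
| 2–11 | 10 | none | no |
| 12–22 | 11 | Week 2 | no |
| 23–43 | 21 | Week 4 | no |
| 44–71 | 28 | Week 8 | no |
| 72–84 | 13 | Week 12 | yes |

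Lost from Week 12: 10 + 11 + 21 + 28 = 70 of 83 days (84%). Kept: 13 of 83 (16%). The Week 12 window itself runs on to Day 98.

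**2. How many subjects.** Protocol 2.1 gives overall discontinuation of 15.3% (NI-MC301) and 17.2% (NI-MC302). It gives no timing and no split by arm. Assume that all exits precede Week 12, that exit days are uniform over Days 2 to 84, and that every leaver attends ET1. Then lost = 850 × rate × 70/83.

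| Rate of exit before Week 12 | Leavers | Lost from Week 12 | Kept |
|---|---|---|---|
| 5% (assumed) | 42.5 | 36 | 7 |
| 10% (assumed) | 85 | 72 | 13 |
| 15.3% | 130 | 110 | 20 |
| 17.2% | 146 | 123 | 23 |

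The last two rows are upper-end scenarios, because overall discontinuation includes exits after Week 12 and some leavers will not attend ET1. The uniform timing is itself an assumption: if every exit fell before Day 72, all 130 to 146 would be lost.

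**3. Two ratings from the same early day.** Protocol 7.2.5 asks for Week 12/ET assessments when study drug is stopped for suspected allergic contact dermatitis. Protocol 6.8.1 keeps subjects whose treatment is stopped for an AE in the study. Such a subject has no Study Exit form that day, so SAP 7 labels the rating Week 12 whatever its study day. A subject who leaves the study on that same day has the rating mapped away. Whether the rating counts therefore depends on a form, not on when it was made. If the first subject later attends the scheduled Week 12 visit, there are two Week 12 records, and the SAP 7 closest-to-target rule covers only unscheduled records.

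**4. ET2.** By eCRF label, an ET2 rating stays with Week 24. By study day, Days 99 to 154 would go to Weeks 16 and 20, and only Days 155 to 182 to Week 24. SAP 7 motivates the exception by the shared Week 12/ET form and does not mention ET2, so the text does not settle which applies.

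**The case against.** The best defence is that a Day 30 rating is not a Week 12 rating, and declining to label it so is sound practice. That stands, and it is why the Week 12 rows should stay as they are. It does not explain why a collected exit rating should appear in no summary. SAP 13.5 already has a suitable device for the physical examination, a shift from Baseline to end of treatment.

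It is also true that the ratings are listed for the ITT population (Listings 16.2.6.4 and 16.2.6.5) and that disposition is tabulated by arm, including reasons for discontinuation before Week 12 (SAP 9.1). The table shells are in a separate file, so missing counts may be planned there. This reduces the importance of the point but does not remove it.

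A reader might infer more than the documents support:

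- **That the Week 12 ratings cover completers only.** ET1 ratings on Days 72 to 98 are kept, as are forms with no same-day Study Exit form. Subjects who leave after Week 12 already have a Week 12 rating.
- **That Week 24 has the same loss.** Re-mapping of ET2 is not established. Subjects who exit at ET1 have no Week 24 rating because none is collected.
- **That the omission favours SB206.** The earlier TEAE figures (SB206 (7 + 17)/(235 + 237) = 24/472 = 5.1%; vehicle (1 + 1)/(116 + 117) = 2/233 = 0.9%) are study drug stops, not study exits. Protocol 6.8.1 and 7.2.6 encourage these subjects to continue visits. Exits by arm are not given, nor are improvement rates from which a bias in points could be calculated.

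**Conclusion.** The point holds in a narrow form. An ET1 global rating before Day 72 with a same-day Study Exit form is left out of the Week 12 summaries by a stated rule, and nothing in the SAP brings it back. About 110 to 123 of 850 subjects would be affected under the upper-end assumptions above, and about 36 to 72 if 5% to 10% leave before Week 12. The direction and size of any bias in the arm comparison are unknown. If leavers rate themselves as completers do, there is none.

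The endpoints are exploratory, summarized descriptively, and outside the fixed testing sequence of SAP 10.7. The primary analysis, alpha and power are not affected. This is an inexpensive improvement, not a threat to the trial's conclusions.

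**What to change.** In SAP 7 and 11.3, before the Week 12 freeze and unblinding described in SAP 6:

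- For the four global assessments, add an 'End of treatment (Week 12 or ET1)' row that uses the termination-visit rating whatever its study day. Keep the Week 12 rows.
- Beside the Week 12 and Week 24 rows, show the number missing by arm over the ITT population.
- State whether ET2 ratings are assigned by eCRF label or by study day.
- Reconcile the SAP 7 rule for forms with no same-day Study Exit form with the early Week 12/ET assessments in Protocol 7.2.5, and say which record is used if a scheduled Week 12 visit follows.

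The cost is some SAP wording and a few added lines in Tables 14.2.3.9.1 and 14.2.3.10.1, with no new data. ET1 ratings reflect shorter follow-up, which the row label discloses. The added row will not restore early leavers to the plots against Week 12 lesion change, because their ET1 lesion counts are mapped by the same rule.

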6.8.3 Withdrawal from Study

A subject/caregiver may voluntarily withdraw from study participation at any time. If the subject/caregiver withdraws consent and discontinues from the study, the investigator will attempt to determine the reason for discontinuation and record the reason in the subject's study records and in the study database. In the event of discontinuation from the study prior to the

Week 12 visit, every effort should be made to have the subject return to the study site to complete the Week 12 evaluations (ET1 visit). If the subject/caregiver is unable or unwilling to return to clinic for the Week 12 visit, the investigator should discuss with the medical monitor the option to perform a remote Week 12 visit. All premature discontinuations and their causes must be carefully documented in the subject's study record and in the study database.

All Week 12 evaluations should be performed at the time of premature discontinuation as applicable if the subject discontinues prior to Week 12. If the subject discontinues after the Week 12 visit, the Week 24 evaluations should be performed. All data gathered on the subject prior to termination will be made available to the CRO. The investigative site should make all reasonable efforts to ensure the subject returns to complete the termination visit, even if the subject is not able to attend other study visits.

Study completion or reason(s) for discontinuation from the study as listed in the study record will be entered into the study database as follows:

- Withdrawal of Consent by Subject/Caregiver
- Lost to Follow-Up
- Adverse Event
- Other

Novan has the right to terminate or stop the study at any time. Should this be necessary, the investigator will ensure that proper study discontinuation procedures are completed.

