10.3 Testing Procedures

10.3.1 Analysis of the Primary Efficacy Endpoint

The primary efficacy endpoint for this study is the proportion of subjects achieving complete clearance of all treatable molluscum lesions at Week 12 for the ITT population. Complete clearance of all MC at Week 12 is defined as having a lesion count of 0 at Week 12. The number and percentage of subjects with complete clearance at Week 12 will be summarized by treatment group.

The primary efficacy endpoint will be analyzed using a generalized estimating equation (GEE) for logistic regression with an exchangeable working correlation structure. The model will include treatment, investigator type (dermatologist vs other), Baseline BOTE score (no inflammation (BOTE = 0) vs. mild/moderate/severe inflammation (BOTE \geq 1) and number of randomized subjects per household (1 subject per household vs. 2 subjects per household), age and Baseline lesion count as factors. The odds ratio between SB206 10.3% and vehicle gel, 95% CIs for the odds ratio, and P-value for the covariate-adjusted treatment comparison will be presented; together with predicted proportions along with their associated 95% confidence interval. Only subjects who achieve complete clearance at Week 12 will be counted as responders for the primary analysis. Subjects who discontinue the study before the Week 12 analysis visit for any reason will be considered not to have achieved complete clearance at Week 12, even if the subject discontinues after a lesion count of 0.

As a sensitivity analysis, the primary efficacy analysis will also be applied to the PP population. Additional sensitivity analyses may be performed including analyses that utilize alternative assumptions from those of this primary method to ensure that efficacy results are not driven by the method of handling missing data.

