## 10.4 Handling of Dropouts or Missing Data

In analyses based on response, a missing response will be considered a non-responder.

For a sensitivity analysis, subjects with missing lesion count at Week 12 but who demonstrated complete clearance at the last collected lesion assessment will be counted as responders.

An additional sensitivity analysis using multiple imputation will be performed to address subjects with missing lesion count at Week 12. A monotone imputation model will be utilized in the following steps:

1. The lesion count data will be imputed to follow a monotone missing data pattern using the Markov chain Monte Carlo method for 10 imputations.
2. Each of the 10 imputations will then be imputed a further 10 times using a monotone regression method to impute the remaining missing data and the Week 12 lesion count using lesion count assessments at Weeks 2, 4, and 8, treatment group, investigator type (dermatologist vs other), BOTE score at Baseline (no inflammation [BOTE=0] vs mild/moderate/severe/very severe inflammation [BOTE $\geq$ 1]), age (0 to <3, 3 to <4, 4 to <5, 5 to <6, 6 to <7, 8 to <9, 9 to <12, and  $\geq$ 12 years old), and baseline lesion count as covariates.

3. Complete Clearance at Week 12 will be re-derived based on the imputed values and then analyzed using the primary analysis model. The results of the 100 analyses will be transformed into a normal statistic and combined into a single analysis using PROC MIANALYZE.

The ROUND and MINIMUM options will be utilized in Steps 1 and 2 to ensure imputed values are non-negative integers. The seed to be used is 20200727.

For subjects with a missing lesion count at Week 12 and identified as “Lost to Follow-up” by the investigator, the following sensitivity analysis will be performed. These lost to follow-up subjects will be contacted to obtain a patient reported outcome of MC disease status at the end of their study participation of either ‘Resolved (no lesions left)’, ‘Resolving (number of lesions decreasing)’, ‘Unchanged (number of lesions similar to previous clinic visit)’, or ‘Worsening (number of lesions increased)’. A reported response endpoint will be derived in the following manner:

- If a subject has a Week 12 lesion count assessment, then the subject will be deemed a responder if the count was 0.

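### SAP Section 7 treats a record on the shared Week 12/ET form as Week 12, at any study day, unless a Study Exit form has the same date, so the derivation can miss the protocol's non-responder rule

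*SAP*

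**What the plan says.** **SAP Section 7 (Analysis visits).** Data are analysed by eCRF visit label. Because Week 12 and Early Termination share a form, each record is checked against the Study Exit form. A record recognised as early termination goes to the study-day table: "If the visit is an Early Termination visit, then the visit will be mapped according to the table below". In that table Week 12 is Day 72 to 98. Every other record takes the default: "If there is no corresponding Study Exit form on the same date, then it will be considered a Week 12 visit". The table is otherwise used only to bring in an unscheduled visit where a visit has no assessment. There are two tie-breaks. An in-clinic count beats a remote one in the same window, and a nearest-to-target rule applies "In the event of multiple unscheduled records falling in the same analysis window".

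**Protocol 10.3.1.** "Complete clearance of all MC at Week 12 is defined as having a lesion count of 0 at Week 12". It adds: "Subjects who discontinue the study before the Week 12 analysis visit for any reason will be considered not to have achieved complete clearance". This holds even where the last count was 0.

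**Protocol 6.8.3.** The Week 12 evaluations are due when a subject discontinues early. Sites are also asked to bring back subjects who have already discontinued, to complete the ET1 visit.

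**Protocol 7.2.5 and 6.8.1.** Week 12/ET assessments are done when drug is stopped for suspected allergic contact dermatitis. A subject whose treatment is stopped for an adverse event stays in the study and is encouraged to attend later visits, Week 12 in particular.

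**SAP 10.4.** "In analyses based on response, a missing response will be considered a non-responder". The multiple-imputation analysis "will be performed to address subjects with missing lesion count at Week 12".

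**The concern.** The same-date test works for a completer, whose exit form is dated at Week 24, and for a discontinuer whose ET1 visit and exit form share a date. It fails when those two dates differ. A subject might withdraw on Day 40 and return for ET1 on Day 47, or the exit might be recorded some days after the visit. The ET1 count is then labelled Week 12 although the subject left weeks earlier.

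A mislabelled zero is not missing, so SAP 10.4 does not turn it into a non-response. No other SAP sentence applies the protocol's discontinuer rule to it. The primary endpoint and both responder-type Week 12 secondary endpoints (count of 0 or 1, and at least 90% reduction) draw on the same value. The missing-data analyses in SAP 10.4 leave it unchanged, because they act only on missing Week 12 counts. Double programming (SAP Appendix B) shows that two datasets agree with each other, not that the rule agrees with the protocol.

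**Working it through.** **1. Two routes by which an early count becomes Week 12**

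| | (a) Study discontinuer | (b) Drug stopped for suspected contact dermatitis, subject stays in study |
|---|---|---|
| Form | ET1, any study day | Week 12/ET assessments, if entered on the shared form (eCRF not available to check) |
| Same-date exit form | Only if the dates happen to match | Not expected |
| SAP 7 label if none | Week 12 | Week 12 |
| Protocol 10.3.1 discontinuer rule | Applies: non-responder | Does not apply |
| If a true Week 12 visit follows | Does not arise | No rule chooses between the two records |
| Effect | Can only add responders | Either way |

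**2. The plan's own figures.** Both documents give 425 per arm, 20% vs 29.5%, two-sided 0.05 and 90% power.
- Pooled SE = √(2 × 0.2475 × 0.7525 / 425) = 0.0296; unpooled SE = √((0.20 × 0.80 + 0.295 × 0.705) / 425) = 0.0294.
- Power = Φ((0.095 − 1.96 × 0.0296) / 0.0294) = 89.6%, which reproduces the stated 90%.
- One subject is 1/425 = 0.24 point in an arm.

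**3. Size of route (a).** The inputs are the study discontinuation rates of 15.3% (NI-MC301) and 17.2% (NI-MC302) in Protocol 2.1, and the Week 8 clearance rates of 15.3% vs 10.3% and 13.9% vs 5.9% in Protocol 2.1.4.3. Two assumptions are needed: that these clearance rates apply to early leavers, and what share is mislabelled. The discontinuation rates may include exits after Week 12.
- Discontinuers per arm: 425 × 15.3% = 65.0; 425 × 17.2% = 73.1.
- 5% mislabelled (3.3-3.7 per arm): zeros 0.50 vs 0.33 and 0.51 vs 0.22, a shift of 0.04-0.07 point.
- 10% mislabelled (6.5-7.3 per arm): zeros 0.99 vs 0.67 and 1.02 vs 0.43, a shift of 0.08-0.14 point.
- All mislabelled: 65.0 × (15.3% − 10.3%) = 3.25 net responders (0.77 point); 73.1 × (13.9% − 5.9%) = 5.85 (1.38 points).

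**4. Upper bound for route (b).** Take every drug stop for a TEAE in Protocol Table 2: SB206 7/235 and 17/237, vehicle 1/116 and 1/117. Per 425 that is 12.7 and 30.5 vs 3.7 and 3.6. Suspected contact dermatitis is only part of these. For comparison, Table 4 shows contact dermatitis in 6/237 on SB206, about 11 per 425.
- No later Week 12 count: 12.7 × 15.3% − 3.7 × 10.3% = +1.56 (+0.37 point); 30.5 × 13.9% − 3.6 × 5.9% = +4.02 (+0.95 point).
- Early count replaces a later one, using the prior Week 12 rates: 12.7 × (15.3% − 25.8%) − 3.7 × (10.3% − 21.6%) = −0.92 (−0.22 point); 30.5 × (13.9% − 30.0%) − 3.6 × (5.9% − 20.3%) = −4.39 (−1.03 points).

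**5. Could this change the conclusion?** Unadjusted pooled z-test with 85 of 425 vehicle responders:

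| SB206 responders | p |
|---|---|
| 125 (planning effect) | 0.0015 |
| 119 (125 less the route (a) ceiling of about 6) | 0.0063 |
| 109 | 0.0498 |
| 108 | 0.060 |

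The boundary of 109 vs 85 is 24/425 = 5.65 points, in line with the 5.7% lowest detectable difference in SAP Section 5. There, one relabelled subject decides the result. At the planning effect, even the route (a) ceiling does not.

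**The case against.** A reader might infer that the SAP replaces the protocol's rule with a laxer one. The documents do not support that. SAP Section 14 declares no change to protocol methodology. The SAP 11.1 sensitivity analysis that credits cleared discontinuers makes sense only if the primary analysis does not credit them. So for route (a) the defect is a failure to implement, not a contradiction of intent. It remains a defect, because the derivation as stated can give the wrong label.

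Other points on that side:
- **Matching dates are the designed case**, since Protocol 6.8.3 places the evaluations at discontinuation. This stands. How often dates differ is not in the documents, and the 5%-10% is an assumption.
- **The Week 12 analysis visit is not wholly undefined.** The SAP 7 table has an analysis-visit column giving Day 72 to 98. This largely stands. What needs confirming is that Protocol 10.3.1 means that window, because an exit on Day 72-79 falls inside it but before the scheduled visit window (Day 80-90).
- **The planned analyses already bound route (a).** The last-count analysis in SAP 11.1 is mandatory and roughly reports the upper limit. This stands, but it does not give the strict figure that the protocol asks for. The SAP 11.1 dropout scenarios would reach a mislabelled subject only if dropouts are taken from disposition, which is the natural reading but is not stated.
- **Route (b) depends on an eCRF that cannot be seen.** This stands; it is conditional.
- **Visit-label analysis is legitimate**, and a strict day limit could move a genuine early Week 12 visit. This stands, and is why the limit below is Day 72 rather than Day 80.

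**Conclusion.** The labelling rule is wrong as written. The same-date test with no day limit can turn an early-termination count into the primary Week 12 value, and the SAP does not apply the protocol's non-responder rule to that value. If the contact-dermatitis assessments go on the same form, it can do the same for subjects whom that rule does not cover.

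The effect is probably small. Route (a) moves the difference by about 0.04-0.14 point if 5%-10% of discontinuers are mislabelled, with a ceiling of 0.8-1.4 points. Route (b) lies within about −1.0 to +0.9 point even at its upper bound. These sizes assume that the earlier studies' discontinuation and clearance rates carry over. The number actually affected and the net direction are unknown, so a reader should not infer a known bias towards SB206. The rule matters only for a result near the boundary. It is still worth correcting because it governs the primary endpoint and the correction is cheap.

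A reader might also fold remote-only zeros into this point. That is a separate and minor wording conflict. Protocol 7.1.1 allows complete clearance to be confirmed only in clinic, while Protocol 10.3.1 and SAP 10.1 require only a count of 0.

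**What to change.** Before the Week 12 unblinding described in SAP Section 6:
1. **Identify ET visits from disposition** (study discontinued before Week 12), whether the exit form is dated before, on or after the visit. SAP 9.1 already uses this information for its summaries.
2. **State the Protocol 10.3.1 rule in SAP 10.4 and 11.1** for the primary and the responder-type secondary endpoints. Confirm that the Week 12 analysis visit means Day 72-98, and say how exits on Day 72-79 are treated.
3. **Map any Week 12/ET form dated before Day 72 by its study day**, and give a later true Week 12 visit precedence.
4. **Separately and minor:** reconcile Protocol 7.1.1 with Protocol 10.3.1 and SAP 10.1 on remote-only Week 12 zeros, and make the optional in-clinic-only analysis in SAP 10.4 definite.

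The cost is SAP wording and slightly more dataset programming, with no new data. The downside is that a few early clearances may become non-responses, including a rare genuine Week 12 visit held before Day 72.
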